Trial 1. In Trial 1 (Acceptability) we will gather acceptability and usability data from up to 30 therapists. After being consented therapists will complete a packet of information about how they treat child anxiety and their beliefs about treatment related issues. Each therapist will then receive training from a study intervention specialist on how to use Mayo Clinic Anxiety Coach. The therapists will be given access to use Mayo Clinic Anxiety Coach and be given an iPod Touch and can incorporate it into their practice as they desire for a period of six months during which time the therapists will have access to the intervention specialist to answer questions about how to use the application. To protect patient confidentiality, the system will generate numerical identifiers (e.g. Patient #1) and therapists will only be able to enter ages into the system, rather than full names and birthdates. Therapist will be asked to complete questionnaires about how they treat child anxiety and their beliefs about treatment related issues as well as questionnaires about usability and how they integrated Anxiety Coach into their practice two weeks and six months after completing the training. In addition, data automatically recorded through any use of the application will be analyzed.

Trial 2. In Trial 2 (Increasing Exposure Use) 30 therapists will be randomized to treat 30 children with anxiety disorders with treatment as usual or FTF-AC. (If necessary due to limited therapist availability, therapists randomized to TAU will treat a second patient with FTF-AC). Therapists and patients/parents will be consented. Data collection will include questionnaires completed by therapists, patients, and parents before and after treatment, as well as audio recordings of sessions, and data automatically saved by the application.

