C.10.b.2. Aim 2: Assess feasibility, safety, acceptance, and impact of *Anxiety Coach*. Analyses for Trial 1 will consist of examining changes in therapist questionnaires via repeated measures analyses of variation and descriptively summarizing data on therapist use and ratings of acceptability. Most appropriately for the present design of Trials 2 and 3, descriptive statistics will be calculated on all fidelity (e.g., frequency of exposure), feasibility (e.g., quantity and content of communication between the therapist and project director, frequency of assessing the application), and clinical variables (e.g., means, standard deviations, percentage of patients continuing to meet diagnostic criteria). Consistent with the ultimate goal of generating estimates of the effect of *Anxiety Coach*, symptom change within Trials 2 and 3 will be compared between groups using repeated measures analysis of variance (RMANOVA) and the frequency of the therapists' use of exposure will be compared between the TAU and FTF-AC condition using analysis of covariance (ANCOVA) to control for diagnosis and symptom severity. Given that this project aims to test the feasibility of a fully powered RCT, analyses testing group differences will be considered exploratory. Although the use of RMANOVA and ANCOVA has significant limitations (i.e., the treatment of missing data), the small sample size and inclusion of multiple therapists does not permit the use of a more powerful statistical approach such as a mixed-effects regression model. However, exploratory analyses using mixed-effects regression model will be conducted. These analyses will be completed to assist in planning design and analysis of a fully powered RCT, rather than to provide interpretable results.

C.10.b.3. Aim 3: Develop a protocol for implementing *Anxiety Coach*. To develop a protocol for using *Anxiety Coach* to increase therapist fidelity to evidence-based CBT and provide treatment with minimal direct contact, the frequency and timing of contact between the project director and therapists as well as the therapist and patient will be used to construct guidelines for monitoring and interacting with therapists and patients. The questions from patients and therapists will be summarized qualitatively and used to refine *Anxiety Coach* and develop the educational component of the protocol.

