C.10.c. Attrition, Noncompliance and Missing Data. The intention to treat analysis set will serve as the principal analysis set. Attempts will be made to minimize the missing data due to missed visits (i.e., fewer than the required six appointments). To handle missing data the following approach will be used. The analyses of the primary outcome will be performed in two ways: 1) using complete case scenario i.e., those patients that

July 1, 2019 (Version 12)

have data available on both time points and 2) imputing a rank from the earlier time point carried forward. Last rank carried forward has been shown to have better statistical properties than the last observation carried forward approach. In addition to these, we will also explore other sensitivity analysis such as imputation of a mean or median or worst or best case values in the respective groups. Findings from sensitivity analysis will be viewed in light of primary analysis prior to reaching final conclusions and interpretation of the results.

PROTECTION OF HUMAN SUBJECTS

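### The worst/best-case imputation leaves each arm's direction and value undefined; read naturally, with similar dropout, it does not bound the effect of missing data on the arm difference

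*Protocol*

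**What the plan says.** Protocol C.10.c sets the rules for missing data. "The intention to treat analysis set will serve as the principal analysis set". The primary outcome is to be analysed in two ways: on complete cases, and by "imputing a rank from the earlier time point carried forward". The section then adds an open-ended list: "we will also explore other sensitivity analysis such as imputation of a mean or median", or "worst or best case values in the respective groups". The full item reads "imputation of a mean or median or worst or best case values in the respective groups". Findings from these analyses are to be considered alongside the primary analysis before conclusions are drawn.

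The text does not state:

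- which direction each group takes in a given run;
- whether worst and best mean the most extreme value observed in that group or the end of the scale;
- any run in which one group gets its worst value and the other its best.

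The SAP does not mention missing outcomes, so C.10.c is the only rule available to the analyst. Protocol C.10.b.2 compares symptom change between groups by repeated measures ANOVA and calls the group comparisons exploratory. C.10.a says the study is not powered for group differences.

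**The concern.** In the item as written, the reference to the respective groups covers the whole list. For a mean or a median it can hardly mean anything except that each group receives its own statistic. Carried over to worst and best, it suggests that each group receives its worst value in one run and its best in another. Both arms are then pushed the same way, and much of the push cancels in the arm difference.

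The missing-data assumption that most threatens a comparison is that dropouts fared differently in the two arms. A same-direction fill does not represent that. If it agrees with the complete-case result, a reader may take the agreement as robustness when the relevant assumption was never varied. The study's stated purpose is to estimate the effect of Anxiety Coach in preparation for a fully powered trial, so an honest range around the estimate is worth having.

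**Working it through.** **Inputs.** Trial 2: "30 therapists will be randomized to treat 30 children with anxiety disorders with treatment as usual or FTF-AC". An even split of 15 per arm is an assumption. The documents give no dropout rate, so 2, 3 or 5 missing of 15 per arm are assumed. For scale, the 0 to 10 severity rating in Protocol C.9.a is used, with assumed post-treatment means of 5.0 (TAU) and 3.5 (Anxiety Coach). The CGI-I responder definition in C.9.a supplies the binary example; its counts are assumed. The plan has no figure of its own to reproduce.

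**Formula, equal dropout.** Let d be the missing share in each arm, D the complete-case difference (TAU minus Anxiety Coach), and W_T and W_A the values imputed in TAU and Anxiety Coach. Then

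imputed difference = (1 − d) × D + d × (W_T − W_A).

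- Same scale extreme in both arms: W_T − W_A = 0, so the result is (1 − d) × D.
- Each group's own observed extreme: the result equals D only if W_T − W_A happens to equal D.
- Crossed scale extremes: (1 − d) × D ∓ d × 10.

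**Scale extremes, D = 5.0 − 3.5 = 1.5.**

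| Missing per arm | Both worst or both best | Crossed |
|---|---|---|
| 2 of 15 | 0.867 × 1.5 = 1.30 | 1.30 ∓ 1.33 = −0.03 to 2.63 |
| 3 of 15 | 0.80 × 1.5 = 1.20 | 1.20 ∓ 2.00 = −0.80 to 3.20 |
| 5 of 15 | 0.667 × 1.5 = 1.00 | 1.00 ∓ 3.33 = −2.33 to 4.33 |

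**Own-group observed extremes, 3 of 15 missing per arm.** This used 20,000 simulated datasets with an assumed SD of 2.0 and scores rounded and limited to 0–10. Average differences were 1.47 for complete case, 1.47 for both worst, 1.42 for both best, and 0.19 to 2.70 for the crossed runs. In single datasets the both-worst result departed from the complete-case value by −0.47 to +0.45 (5th to 95th percentile). It came within 0.01 in only 2.5% of runs.

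**Responders (Anxiety Coach minus TAU), 8/12 against 5/12, 3 missing per arm.**

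- Complete case: 8/12 − 5/12 = 25 points.
- All missing counted as non-responders: 8/15 − 5/15 = 20 points.
- All missing counted as responders: 11/15 − 8/15 = 20 points.
- Crossed: 8/15 − 8/15 = 0, and 11/15 − 5/15 = 40 points.

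**Unequal dropout, 1 missing in Anxiety Coach and 5 in TAU, scale extremes, same means.**

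- Both worst: (10 × 5.0 + 5 × 10)/15 − (14 × 3.5 + 10)/15 = 6.67 − 3.93 = 2.73.
- Both best: 50/15 − 49/15 = 0.07.
- Crossed: 50/15 − 59/15 = −0.60, and 100/15 − 49/15 = 3.40.

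Here the same-direction runs move the result a good deal, though still not over the full range.

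**The case against.** The strongest reply is that the plan does not prescribe the same direction. The sentence is silent on direction and could be read to allow a crossed fill. It is also one example in an open, exploratory list, so crossed runs are not excluded. The main handling of missing data lies elsewhere, and carrying the rank forward already makes a different assumption from complete case. Dropout need not be equal either: Protocol C.7.e plans to compare premature discontinuation between conditions, and the unequal-dropout example shows the listed check moving the result. All of this stands, and it limits the point to an underspecified rule of minor weight.

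It does not remove the point. If the sentence is merely silent, the directions still have to be stated. Carrying the rank forward applies one rule to both arms, so it does not represent dropouts faring badly in one arm and well in the other either.

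A reader might infer that the same-direction check simply reproduces the complete-case difference. That is too strong. It is exact for imputation of each group's own mean. With own-group extremes it holds only approximately and on average, and single small trials vary. With a common extreme the difference shrinks by the factor (1 − d), as from 25 to 20 points above.

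**Conclusion.** The point holds as a minor one. C.10.c does not define the direction or the value imputed in each arm. On the natural reading with similar dropout, the check does not span what missing data could do. At 3 of 15 missing per arm, both same-direction runs with scale extremes give 1.20, against a possible range of −0.80 to 3.20. In the responder example both give 20 points, against 0 to 40. The arm size, dropout, means, SD and responder counts are all assumed; the formula does not depend on them.

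Two wider inferences are not supported. The documents do not say that dropout will be equal, so it cannot be said that the check is uninformative in every case. Nor does a confirmatory conclusion rest on it, because the comparisons are exploratory and the analysis mainly descriptive.

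**What to change.** In C.10.c, replace the worst/best phrase with a rule that does the following:

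- It states, for each outcome, whether worst and best are the group's observed extremes or the ends of the scale.
- It specifies two crossed scenarios: missing Anxiety Coach outcomes set to worst with missing TAU outcomes set to best, and the reverse.
- Optionally, it adds intermediate steps that shift the imputed values in one arm by stated amounts.
- It reports the resulting estimates descriptively beside the complete-case and rank-carried-forward results, without p-values. A tipping threshold is not useful here, because the plan defines no success criterion for the arm difference that could be tipped.

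The cost is a few lines of analysis code and no new data. The drawback is that the crossed bounds will be wide at about 15 per arm, which is the reason for the optional intermediate shifts.

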4.1.1 Risks to Human Subjects

4.1.1.a. Human Subjects Involvement, Characteristics, and Design: Participants and their involvement will include: 1) community therapists responding to a survey, conducted under IRB 14-002608, of practice characteristics and beliefs during Phase I; 2) 30 community therapists receiving training and providing usability data in Phase II, Trial 1; 3) 40 therapists affiliated with institutions providing study intervention (Phase II, Trials 2 and 3); and 3) 75 children with an anxiety disorder ages 7 to 17 and one or more caregivers, anticipated to be up to 60 years of age, receiving study intervention (15 in Phase I, 60 in Phase II Trials 2 and 3). Children below the age of 7 will be excluded because they are deemed too young to safely and effectively engage with the study materials. There are no restrictions on ethnicity, social background, or gender. Study participation is entirely voluntary and participants may withdraw from the study at any time without penalty.

The inclusion of community therapists is necessary to characterize the state of community mental health and to test the feasibility of the study intervention for disseminating evidence-based treatment to community/non-specialty settings.

The inclusion of children with an anxiety disorder and a caregiver is necessary to examine the feasibility of improving treatment outcome for children with anxiety disorders. The project includes children, a special population, because this population is particularly at risk for not receiving evidence-based care and the project's aim is to improve access to cognitive behavioral treatment for childhood anxiety disorders. Children will be recruited through participating community therapists to maximize the external validity of the study as a test of the intervention's feasibility for improving care in community, non-research settings. Parents will provide consent for themselves and their child to participate. Children will provide assent.

4.1.1.b. Sources of Materials: Research material will be collected from the therapist survey respondents from IRB 14-002608, study therapists, child patients and their caregivers.

The information collected through the therapist survey materials will include demographics, frequency of treating patients with anxiety disorders, frequency of using a variety of therapy strategies, beliefs about exposure therapy, opinions regarding the usability of the application, and report of how often and why they chose to use the application. Responses to the survey will be initially individually identifiable to allow recruitment of eligible therapists into Phase II. Only the staff at survey research center (SRC) will have access to this individually identifiable data, which will not be shared with the project researchers or other study staff.

Following consent, but prior to participation in Phase II Trials 2 and 3, eligible therapists will be asked to provide evidence of licensure with no disciplinary action. This information will be obtained by the study coordinator and will not be shared with other individuals including other study staff and researchers. Additional material will include therapist-provided audio recordings of treatment sessions that the independent evaluators use to code the therapists' use of treatment principles. The recordings will not be identifiable (i.e., they will be labeled with code numbers described below). The final material collected from therapists will include re-administration of the beliefs about exposures questionnaire from the survey in IRB 14-002608.

Material collected directly from the participants (child and caregiver) will be responses to behavioral ratings scales, psychiatric interviews, data entered into the Anxiety Coach application, and session content from audio recordings. The therapy sessions will be recorded by the therapists, transferred to the study team via the secure intervention web-portal, labeled with a code number (see below) by the study coordinator, and coded by the independent evaluators. All other data will be collected and entered by the independent evaluators.

Appropriate steps will be taken to ensure the confidentiality of data from survey respondents, study therapists, patients, and parents. To begin with, participants (therapists, patients, and caregivers) will be assigned study codes that are not based on the individual's information. All written, electronic, and audio recording material and data will be identified only by code. The key linking participants to study codes will be kept in a locked cabinet separate from the data. All paper-generated data will be stored in locked files in the office of [name]. All computer-generated data will be maintained in password-limited, secure network drive files. All identifiable information from the survey will have the same level of protection with the addition of being managed by SRC and not made available to the study staff. To protect patient confidentiality, only

authorized persons at Mayo Clinic and the Institutional Review Board will have the right to review research records. Confidentiality of those records will be protected to the extent permitted by law. Research records will be kept separate from identifying information in a locked cabinet and will not be released without the participant's consent unless required by law. Identifying information will be removed prior to publication and presentation of the study results. The Anxiety Coach application will not have any fields that request identifiable in Phase I or II, Trials 1, 2, or 3.

4.1.1.c. Potential Risks: The risks of participating in this project are considered to be minimal and include completing relatively lengthy research measures, the potential to be randomized to a condition with less effective treatment, and breach of confidentiality. The methods to address these potential risks are outlined below in Section 4.1.2.b.

One potential risk of participating in this project includes discomfort during the data collection (survey, phone screenings, and assessments) related to discussing sensitive topics and the length of the evaluation. However, the length of material completed by therapists are minimal and the patients in the study are seeking treatment and presumably are interested in discussing their symptoms with an expert clinician. It is estimated that the survey will require 20 to 30 minutes to complete, and the patient interview and questionnaire completion will take approximately 2-3 hours for the initial evaluation and 1-2 hours for the post-treatment assessment. Having the family complete questionnaire packets at home where the family can work at their own pace and take breaks will minimize the burden associated with lengthy assessments.

Although difficult to predict with certainty, the degree of risk and benefit may differ among the three conditions. Neither the relative benefit of augmenting face-to-face therapy with *Mayo Clinic Anxiety Coach* nor the relative risk of minimal contact treatment have yet been tested, and so the relative cost-benefit ratios are uncertain. The risk of being randomized to TAU is that the patient may receive a potentially less effective treatment. However, as this treatment is the standard intervention outside the study, participation in the study will not have a detrimental effect on the quality of the patient's treatment. In fact, the study requirement of a minimum of 6 sessions will likely result in a higher level of care. Further, there is no portion of the study during which patients will be asked to receive no treatment. Alternatively, patients in the minimal contact *Anxiety Coach* condition may be at risk of receiving a less effective treatment because of the decreased therapist contact. However, the goal of the study is to examine the feasibility of minimal contact treatment. Thus, patients may receive emergent care or more frequent contact if needed. Such occurrences will be collected as measures of tolerability. Within all conditions if additional care is clinically indicated the therapist (with the assistance of the study staff under the direction of [name]) will assist the family in making arrangements for appropriate care.

More generally, the study includes potential risks related to psychotherapy. In rare cases psychotherapy may exacerbate symptoms. Should a patient's symptoms increase significantly anytime during the study and require discontinuation of study treatment, families will be connected with appropriate alternative treatments outside the study protocol including psychotropic medication, additional psychotherapy, or hospitalization. In addition, as with all treatment, the therapists will closely monitor the patient's emotional well-being and pace therapy appropriately (i.e., recommending a slower pace or "exposure breaks"). The therapists will also monitor parent-child interactions and the parent's emotional state to determine if further action is indicated. Moreover, the study therapists will have access to the intervention specialists in all conditions as an additional resource for protecting patients against harm.

The confidentiality of therapists, in addition to patients (children and caregivers), will be maintained through the procedures described above in Section 4.1.1.b. To minimize risk, identifiable information from the survey will only be available to the SRC. However, therapist's inclusion in the pool of providers eligible for participation in Phase II implies an endorsement of openness to CBT and infrequent use of exposure. However, this is thought to pose a limited risk as previous research suggests such responses will be the norm. During recruitment, the structure of phone screenings will allow therapists to decline participation in a manner that does not imply a history of disciplinary action.

